### RATIONALE FOR THE AMENDMENT

The primary purpose of this protocol amendment is to align with modifications made to the Paediatric Investigation Plan. The primary changes include:

- A new categorization for main primary and secondary endpoints key binding element was proposed in order to ensure reporting compliance with registries (EudraCT, clinicaltrials.gov). This categorization does not affect the type or processing of data collected and reported in the study report as they will be assessed as initially planned.
- UCB also took the occasion to provide further clarification to the study duration as well as the primary, secondary, and other variables wording and categorization.

In addition, language specifying applicable study conduct modifications due to the COVID-19 pandemic has been added.

Furthermore, minor administrative changes have been done, including the update of the study team and minor editorial corrections to correct typographical errors and to update document abbreviations.

### MODIFICATIONS/CHANGES

- The name and contact information for the Clinical Program Director, Clinical Project Manager, Clinical Trial Biostatistician, and Medical Director (Medical Therapeutics) were updated.
- Reorganization and clarification of the study variables and corresponding statistical analyses sections was completed.
- Text added to allow 100 subjects to enroll in SP848 from EP0060.
- Text added to identify the subjects directly enrolling from sites in Japan and China.
- Text added to clarify study conduct due the COVID-19 pandemic.
- Text updated to clarify the study duration.
- Text updated to clarify that the Safety Follow-Up Visit or the Safety Follow-Up telephone contact is not required for subjects who participate in EP0151 or EP0152.

### REFERENCE

*Contact information for the Clinical Program Director, Clinical Project Manager, Clinical Trial Biostatistician, and Medical Director (Medical Therapeutics) were updated. Original text:*

**Medical Director (Medical Therapeutics):**

Name: [REDACTED] MD

Address: UCB BIOSCIENCES, GmbH  
[name]  
[name]  
GERMANY

Phone: [REDACTED]

E-mail: [REDACTED]

*Serious Adverse Event Reporting phone numbers and emails were updated. Original text:*

Serious adverse event reporting (24h)	
Fax	Europe and Rest of the World: [contact] USA and Canada: [contact] or [contact]
Email	Global: [contact]

*Were revised as follows:*

Serious adverse event reporting (24h)	
Fax	Europe and Rest of the World: [contact] USA and Canada: [contact] or [contact] Japan: [name]

Email	Europe and Rest of the World: [contact] or [contact]  Japan: [contact]
-------	---

*Clinical Study Protocol, Section 1 (Summary). Original text, second, third, and fourth paragraphs:*

SP848 was originally designed as an open-label extension study for pediatric subjects in SP847 with partial-onset seizures. SP848 is now amended to be open to subjects who participate in other LCM pediatric clinical studies, including partial-onset seizures and other epilepsy syndromes.

In addition, at selected sites, beginning with Protocol Amendment 4, up to approximately 100 eligible pediatric subjects  $\geq 4$  years to  $\leq 17$  years of age with partial-onset seizures (deemed appropriate for treatment with adjunctive LCM) who have not previously participated in a LCM clinical study will be permitted to enroll directly into SP848. The purpose of enrolling these subjects directly into SP848 is to obtain sufficient long-term safety exposures in the age range of  $\geq 4$  years to  $\leq 17$  years of age; the long-term safety data will be included in planned regulatory submissions for LCM as adjunctive therapy for partial-onset seizures in pediatric subjects  $\geq 4$  years to  $\leq 17$  years of age with epilepsy.

Protocol Amendment 6 allows up to approximately 75 additional eligible pediatric subjects with epilepsy who participated in EP0060 to enroll into SP848. In addition, subjects already enrolled in SP848 may participate in EP0060, if eligible, and then resume participation in SP848. These subjects may either voluntarily choose to have an iv LCM infusion even though they are capable of taking oral LCM or require iv LCM infusion due to a medical reason or procedure (ie, unable to take oral LCM).

*Were revised as follows:*

SP848 was originally designed as an open-label extension study for pediatric subjects in SP847 with partial-onset seizures. SP848 is now amended to be open to subjects who participate in other LCM pediatric clinical studies, including partial-onset seizures and other epilepsy syndromes. SP848 includes subjects  $\geq 1$  month to  $\leq 18$  years of age since subjects who complete SP847 or another applicable LCM pediatric epilepsy study in subjects  $<18$  years of age may have aged to 18 years old by the time they complete that study and enroll in SP848.

In addition, at selected sites, beginning with Protocol Amendment 4, up to approximately 100 eligible pediatric subjects  $\geq 4$  years to  $\leq 17$  years of age with partial-onset seizures (deemed appropriate for treatment with adjunctive LCM) who have not previously participated in a LCM clinical study will be permitted to enroll directly into SP848. Beginning with local Protocol Amendment 5.2 for sites in Japan, approximately 46 eligible pediatric subjects  $\geq 4$  years to  $\leq 17$  years of age with partial-onset seizures who have not previously received LCM will directly enroll at approximately 9 sites in Japan. Beginning with local Protocol Amendment 5.4 for sites

in China, approximately 60 additional eligible pediatric subjects with partial-onset seizures aged  $\geq 4$  years to  $\leq 17$  years, who have not previously participated in a LCM clinical study, will enroll directly into SP848. The purpose of enrolling these subjects directly into SP848 is to obtain sufficient long-term safety exposures in the age range of  $\geq 4$  years to  $\leq 17$  years of age; the long-term safety data will be included in planned regulatory submissions for LCM as adjunctive therapy for partial-onset seizures in pediatric subjects  $\geq 4$  years to  $\leq 17$  years of age with epilepsy.

Protocol Amendment 6 allows up to approximately 75 additional eligible pediatric subjects with epilepsy who participated in EP0060 to enroll into SP848. Protocol Amendment 8 allows an enrollment increase from 75 to 100 eligible pediatric subjects  $\geq 1$  month to  $\leq 17$  years of age with epilepsy who participated in EP0060 to enroll in SP848 in order to reflect EP0060's inclusion of subjects down to 1 month of age. In addition, subjects already enrolled in SP848 may participate in EP0060, if eligible, and then resume participation in SP848. These subjects may either voluntarily choose to have an iv LCM infusion even though they are capable of taking oral LCM or require iv LCM infusion due to a medical reason or procedure (ie, unable to take oral LCM).

Approximately 200 subjects who may participate in other LCM pediatric clinical studies in epilepsy will be eligible to participate in SP848. In total, up to approximately 400 subjects may be eligible to participate in SP848.

*Clinical Study Protocol, Section 1 (Summary). Original text, seventh and eighth paragraphs:*

The primary variables for assessment of safety and tolerability are:

- Adverse events (AEs) reported spontaneously by the subject and/or caregiver or observed by the investigator
- Subject withdrawal due to AEs
- Hematology, blood chemistry, endocrinology, and urinalysis parameters
- 12-lead electrocardiograms (ECGs)
- Vital sign measurements (blood pressure and pulse)
- Physical and neurological examination findings
- Body weight, height, and calculated body mass index (BMI)
- Tanner stage (if applicable)
- Plasma concentrations of LCM (for population PK analysis) and concomitant AEDs
- Achenbach Child Behavior Checklist (CBCL) for children 18 months and older (CBCL/1½-5 and CBCL/6-18) assessing behavior
- Bayley-III scales for children  $<18$  months of age at time of enrollment (applicable only to subjects enrolled in English-speaking countries)

- Cognitive function assessments (Behavior Rating Inventory of Executive Function® [BRIEF®]/BRIEF®-Preschool Version [BRIEF®-P]) (if applicable)

The secondary variables include seizure counts (assessed using seizure diaries in order to evaluate preliminary evidence of efficacy during long-term exposure in this population), the Clinical Global Impression of Change, the Caregiver Global Impression of Change, quality of life assessments (Pediatric Quality of Life Inventory [PedsQL™]), health care resource use, and a LCM palatability and ease of use questionnaire.

*Were revised as follows:*

The study variables to be assessed are defined in Section 4.2.

*Clinical Study Protocol, Section 2 (Background Information). Original text, final paragraph:*

SP848 was originally designed as an open-label extension study for pediatric subjects in SP847 with partial-onset seizures. SP848 is now amended to be open to subjects who participate in other LCM pediatric clinical studies, including partial-onset seizures and other epilepsy syndromes. In addition, at selected sites, beginning with Protocol Amendment 4, up to approximately 100 eligible pediatric subjects  $\geq 4$  years to  $\leq 17$  years of age with partial-onset seizures (deemed appropriate for treatment with adjunctive LCM) who have not previously participated in a LCM clinical study will be permitted to enroll directly into SP848. The purpose of enrolling these subjects directly into SP848 is to obtain additional long-term safety exposures in the age range of  $\geq 4$  years to  $\leq 17$  years of age; the additional long-term safety data will be included in planned regulatory submissions for LCM as adjunctive therapy for partial-onset seizures.

*Was revised as follows:*

SP848 was originally designed as an open-label extension study for pediatric subjects in SP847 with partial-onset seizures. SP848 is now amended to be open to subjects who participate in other LCM pediatric clinical studies, including partial-onset seizures and other epilepsy syndromes. In addition, at selected sites, beginning with Protocol Amendment 4, up to approximately 100 eligible pediatric subjects  $\geq 4$  years to  $\leq 17$  years of age with partial-onset seizures (deemed appropriate for treatment with adjunctive LCM) who have not previously participated in a LCM clinical study will be permitted to enroll directly into SP848. Beginning with local Protocol Amendment 5.2 for sites in Japan, approximately 46 eligible pediatric subjects  $\geq 4$  years to  $\leq 17$  years of age with partial-onset seizures who have not previously received LCM will directly enroll at approximately 9 sites in Japan. Beginning with local Protocol Amendment 5.4 for sites in China, approximately 60 additional eligible pediatric subjects with partial-onset seizures aged  $\geq 4$  years to  $\leq 17$  years, who have not previously participated in a LCM clinical study, will enroll directly into SP848. The purpose of enrolling these subjects directly into SP848 is to obtain additional long-term safety exposures in the age range of  $\geq 4$  years to  $\leq 17$  years of age; the additional long-term safety data will be included in planned regulatory submissions for LCM as adjunctive therapy for partial-onset seizures.

*Clinical Study Protocol, Section 4.1.2 (Subjects enrolling directly into SP848). Original text, first and second paragraph, new third paragraph:*

Beginning with Protocol Amendment 4, at selected sites, up to approximately 100 eligible pediatric subjects  $\geq 4$  years to  $\leq 17$  years of age with partial-onset seizures (deemed appropriate for treatment with adjunctive LCM) who have not previously participated in a LCM clinical study will be permitted to enroll directly into SP848.

Subjects who enroll directly into SP848 without previous participation in a LCM clinical study will undergo screening. Eligible subjects will initiate treatment with LCM, and the LCM dose will be titrated to a level to optimize tolerability and seizure control (see Section 4.4.1). Subjects will be able to receive LCM oral solution or LCM tablets for up to 2 years as determined appropriate by the investigator.

*Was revised as follows:*

Beginning with Protocol Amendment 4, at selected sites, up to approximately 100 eligible pediatric subjects  $\geq 4$  years to  $\leq 17$  years of age with partial-onset seizures (deemed appropriate for treatment with adjunctive LCM) who have not previously participated in a LCM clinical study will be permitted to enroll directly into SP848. Beginning with local Protocol Amendment 5.2 for sites in Japan, approximately 46 eligible pediatric subjects  $\geq 4$  years to  $\leq 17$  years of age with partial-onset seizures who have not previously received LCM will directly enroll at approximately 9 sites in Japan. Beginning with local Protocol Amendment 5.4 for sites in China, approximately 60 additional eligible pediatric subjects with partial-onset seizures aged  $\geq 4$  years to  $\leq 17$  years, who have not previously participated in a LCM clinical study, will enroll directly into SP848.

Subjects who enroll directly into SP848 without previous participation in a LCM clinical study will undergo screening. Eligible subjects will initiate treatment with LCM, and the LCM dose will be titrated to a level to optimize tolerability and seizure control (see Section 4.4.1). Subjects will be able to receive LCM oral solution or LCM tablets for up to 2 years as determined appropriate by the investigator.

SP848 includes subjects  $\geq 1$  month to  $\leq 18$  years of age since subjects who complete SP847 or another applicable LCM pediatric epilepsy study in subjects  $<18$  years of age may have aged to 18 years old by the time they complete that study and enroll in SP848.

*Clinical Study Protocol, Section 4.2 (Variables to be assessed). Original text, Section 4.2.1 and Section 4.2.2:*

## **4.2 Variables to be assessed**

### **4.2.1 Primary variables**

Safety and tolerability will be assessed using the following variables:

- Adverse events reported spontaneously by the subject and/or caregiver, or observed by the investigator

- Subject withdrawal due to AEs
- Hematology, blood chemistry, endocrinology, and urinalysis parameters
- 12-lead ECGs
- Vital sign measurements (blood pressure and pulse)
- Physical and neurological examination findings
- Body weight, height, and calculated BMI
- Tanner Stage (if applicable)
- Plasma concentrations of LCM (for population PK analysis) and concomitant AEDs
- Achenbach CBCL at Baseline for children 18 months and older (CBCL/1½-5 and CBCL/6-18) assessing behavior
- Bayley-III scales at Baseline for children <18 months of age at time of enrollment (applicable only to subjects enrolled in English-speaking countries)
- Cognitive function assessments (BRIEF-P/BRIEF) (if applicable)

#### 4.2.2 Secondary variables

Secondary variables include:

- Seizure counts, which will be assessed using seizure diaries in order to evaluate preliminary evidence of efficacy during long-term exposure in this population
- Clinical Global Impression of Change
- Caregiver Global Impression of Change
- Quality of life assessments (PedsQL) (if applicable)
- Health care resource use (concomitant AEDs, medical procedures, health care provider consultations not related to study, hospitalizations not related to study)
- LCM palatability and ease of use questionnaire

*Was revised as follows:*

### 4.2 Variables to be assessed

#### 4.2.1 Safety variables

4.2.1.1 Primary safety variables

The primary safety variables are:

- Incidence of TEAEs
- Incidence of serious AEs (SAEs)
- Subject withdrawal from the study due to TEAEs

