Subjects who complete SP847 or another applicable LCM pediatric epilepsy study and choose to enter this open-label study will begin on the LCM dose they achieved in SP847 or their previous pediatric LCM study. Subjects who discontinued from SP847 due to a dose reduction or status epilepticus, but for whom it is determined medically appropriate to enter this open-label study, will also begin on the LCM dose they achieved in SP847. Subjects who enroll from EP0060 will begin SP848 with an equivalent LCM dose as they last received in EP0060; however, the LCM dose may be further titrated/adjusted to a level to optimize tolerability and seizure control (up to a maximum level as described below). Subjects who meet eligibility requirements and enroll directly into SP848 without previous participation in a LCM clinical study will initiate treatment with LCM, and the LCM dose will be titrated to a level to optimize tolerability and seizure control (up to a maximum level as described below).

*Clinical Study Protocol, Section 2 (Background information). Original text, first paragraph:*

Epilepsy is the second most prevalent neurological disorder in the world. More than 40 million people have epilepsy—about 1% of the world’s population (Dichek, 1999). Although some forms of epilepsy may respond to surgical treatment and others may not require any treatment at all, most patients with epilepsy require appropriate pharmacological therapy (Perucca, 1996). In the past decade, several new options for the medical treatment of epilepsy have been introduced, including novel AEDs and vagus nerve stimulation.

*Was revised as follows:*

Epilepsy is the second most prevalent neurological disorder in the world. It is estimated that almost 70 million people suffer from epilepsy (Ngugi et al, 2011). Although some forms of epilepsy may respond to surgical treatment and others may not require any treatment at all, most patients with epilepsy require appropriate pharmacological therapy (Perucca, 1996). In the past decade, several new options for the medical treatment of epilepsy have been introduced, including novel AEDs and vagus nerve stimulation.

*Clinical Study Protocol, Section 2 (Background information). Original text, fourth paragraph:*

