Subjects who complete SP847 (including discontinuation from SP847 due to a dose reduction or status epilepticus) or subjects from another applicable LCM pediatric clinical study in epilepsy and who choose to enter the open-label study, will begin with an equivalent LCM dose as they last received in the primary study. Subjects will be able to continue on LCM oral solution (syrup) or switch to LCM tablets. During the study, investigators will be allowed to increase or decrease the dose of LCM and/or concomitant AEDs to optimize tolerability and seizure reduction for each subject. The investigator may titrate/adjust the LCM dose to a minimum of 2mg/kg/day (oral solution [syrup]) or 100mg/day (tablet) and a maximum of 12mg/kg/day (oral solution [syrup]) or the corresponding dose levels for the tablet formulation), not to exceed 600mg/day based on body weight, even if the subject's body weight exceeds 50kg. The maximum permitted LCM dose in SP848 is 12mg/kg/day or 600mg/day, whichever is lower. Increases in the LCM dose must occur only during office visits. If needed to optimize tolerability and seizure reduction in selected subjects, concomitant AEDs may be carefully tapered and discontinued to achieve LCM monotherapy. New concomitant AEDs may be introduced as treatment if the medication has been approved by the Regulatory Authorities in the country in which the subject lives. New concomitant AEDs should be added only when the subject has not optimally or adequately responded to a maximum tolerated dose of LCM. When subjects withdraw from the study, it is

recommended that the study medication be tapered gradually in weekly decrements of 4mg/kg/day (oral solution [syrup]) or 200mg/day (tablets) for subjects who have achieved a dose of LCM  $\geq$ 6mg/kg/day (oral solution [syrup]) or  $\geq$ 300mg/day (tablet). A slower taper in weekly decrements of 2mg/kg/day (oral solution [syrup]) or 100mg/day (tablets) is permitted, if medically necessary. In case of an emergency, a faster taper is permitted after discussion with the medical monitor, whenever possible.

*Clinical Study Protocol, Section 4.3.2 (Exclusion criteria). Original text:*

2. Subject meets the withdrawal criteria for the primary study (with the exception of subjects who discontinued due to a dose reduction or status epilepticus), or is experiencing an ongoing serious AE (SAE).

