- j For subjects enrolling from EP0060, these assessments should be completed at Visit 1.
- k Blood samples may be drawn at any time post-dosing with LCM.
- l For female subjects of childbearing potential, serum pregnancy tests will be performed at Visit 1, the Early Termination Visit, and the Final Visit. Urine pregnancy tests will be performed at Visits 2, 3, 4, 5, 6, 7, 8, and 9.
- m The Tanner Stage will be performed only for subjects who are pubescent at Visit 1 or who will enter puberty during the course of the study.
- n Lacosamide for taper will be dispensed only for subjects who achieve a dose of LCM  $\ge 6$ mg/kg/day (oral solution [syrup]) or  $\ge 300$ mg/day (tablet). It is recommended that the LCM dose be tapered gradually in weekly decrements of 4mg/kg/day (oral solution [syrup]) or 200mg/day (tablet). A slower taper of 2mg/kg/day (oral solution [syrup]) or 100mg/day (tablet) is permitted, if medically necessary. In case of an emergency, a faster taper is permitted after discussion with the medical monitor, whenever possible.
- o As applicable
- p For all subjects  $\ge 6$  years of age already enrolled, the "already enrolled" version should be completed at the next clinic visit, and the "since last visit" version should be completed thereafter.
- q The C-SSRS assessment should be completed if the Unscheduled Visit is due to an AE.
- r Ongoing AEs from the primary study will be followed, as well as recording of new AEs during the current study.

*Clinical Study Protocol, Section 16.1 (Table 2 Schedule of study procedures for SP848 [Year 2]). Original table:*

REDACTED COPY

This document cannot be used to support any marketing authorization application and any extensions or variations thereof.

**Table 2.** Schedule of study procedures for SP848 (Year 2)

Study SP848	Year 2								Safety Follow-Up
Visit a	V10	TC b	V11	V12	V13/TermV	ETV c	Unsch Visit d	Final Visit e	TC f
Weeks in study	60		72	84	96				
Concomitant medications	X	X	X	X	X	X	X	X	X
Concomitant AEDs	X	X	X	X	X	X	X	X	X
Physical exam (complete)					X	X		X	
Physical exam (brief)	X		X	X			X		
Neurological exam (complete)					X	X		X	
Neurological exam (brief)	X		X	X			X		
12-lead ECG g			X		X	X	X	X	
Blood pressure and pulse	X		X	X	X	X	X	X	
Body weight and height	X		X	X	X	X	X	X	

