###### **12.1.2.1.1 AEs**

Adverse events will be coded using the Medical Dictionary for Regulatory Activities (MedDRA®), and tabulated by system organ class and preferred term.

Treatment-emergent AEs will be defined as those events which started on or after the date of first SP848 LCM administration, or whose severity worsened on or after the date of first SP848 LCM administration. Adverse events occurring within 30 days after last dose of LCM will be

considered treatment-emergent. The incidence of TEAEs will be presented by system organ class and preferred term. Serious AEs will also be tabulated and listed.

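### A rollover child withdrawn for an adverse event carried over from the primary study at unchanged severity is not counted in the primary withdrawal variable

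*Protocol*

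**What the plan says.** Section 4.2.1.1 (Amendment 8) has three primary safety variables: incidence of TEAEs, incidence of serious AEs (SAEs), and "Subject withdrawal from the study due to TEAEs".

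Section 12.1.2.1.1 defines TEAEs in two limbs. The first is onset: "those events which started on or after the date of first SP848 LCM administration". The second is worsening: "or whose severity worsened on or after the date of first SP848 LCM administration". Events within 30 days after the last dose also count as treatment-emergent.

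Under Section 4.1.1 (Amendment 6), subjects from SP847 or another pediatric LCM study "will begin with an equivalent LCM dose as they last received in the primary study". A footnote on AE reporting in Table 16-1 adds: "Ongoing AEs from the primary study will be followed, as well as recording of new AEs during the current study".

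Section 12.1.2.1 (Amendment 8), where the primary safety variables are taken up for analysis, names only the incidence of TEAEs and of SAEs. It does not mention withdrawal.

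**The concern.** The first study objective is safety, tolerability and PK during long-term exposure. Giving up LCM because an early side effect never went away is a tolerability failure of that kind. For a rollover child the side effect may have begun on LCM in the primary study, before the first SP848 dose. A withdrawal variable tied to TEAEs then leaves that child out, although the drug, the event and the decision to stop are what the variable is meant to capture. The primary withdrawal count would understate discontinuation for AEs, and always in the direction favorable to the drug.

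**Working it through.** No sample size, test or event rate is involved, so the check applies the two-limb TEAE definition to each kind of AE that could lead to withdrawal.

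**Subjects entering from a primary study**

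1. AE starts on or after the first SP848 dose: a TEAE by the onset limb. Withdrawal counted.
2. AE carried over, worsens in severity on or after the first SP848 dose: a TEAE by the worsening limb. Withdrawal counted.
3. AE carried over, non-serious, severity unchanged: meets neither limb. Withdrawal not counted.
4. SAE ongoing at entry: exclusion criterion 2 (Section 4.3.2) bars the child, so the case should not arise.

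**Subjects enrolling directly**

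5. LCM is started at the first Titration Visit within SP848 (Section 5.2). Any AE that begins on LCM therefore has its onset on or after the first SP848 dose and is a TEAE. Withdrawal counted.

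Only case 3 is missed.

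**Can case 3 occur?** Nothing in the text shown rules it out. Section 4.3.3 requires withdrawal for intolerable AEs and does not restrict these to TEAEs. A non-serious ongoing AE does not by itself bar entry, and such AEs are followed in SP848. An AE of constant severity can become intolerable through persistence alone.

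**Size.** Let W be the number of withdrawals due to any AE and c the number of those in case 3. The variable reports W − c, so the relative undercount is c/W. The protocol gives neither W nor c. The effect of one missed case can be shown from the planned total in Section 12.2, up to approximately 400 eligible subjects: 1/400 = 0.25 percentage points. If fewer are treated, each case weighs more.

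**The case against.** The strongest reply has four parts.

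- **The gap is narrow.** The worsening limb rescues carried-over AEs that get worse. Exclusion criterion 2 bars ongoing SAEs and most children who met the primary study's withdrawal criteria. Rollover subjects must also be judged likely to benefit. All of this stands and limits the point to case 3.
- **No information is lost.** Section 4.3.3 requires the eCRF to document the primary reason for withdrawal, and a disposition table may well show it. This stands too. What is affected is the primary variable, which the protocol itself fixes.
- **One TEAE convention for the primary variables is reasonable.** It is for incidence, where an event with onset in another study should not be counted as new. Withdrawal is different, because the decision to stop happens in SP848 whenever the AE began.
- **Amendment 8 says nothing changes.** Its rationale presents the recategorization as leaving data processing and reporting untouched, with assessment as first planned. The superseded variable was "Subject withdrawal due to AEs", which would have counted case 3. A difference from superseded text is not an error. But if the intent was to leave the assessment unchanged, the wording in Section 4.2.1.1 does not achieve it.

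A reader might also infer more than the text supports:

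- That every withdrawal for a carried-over AE is missed. The worsening limb contradicts this.
- That about half the study population is affected. The protocol expects about 200 subjects from other pediatric LCM studies within a total of about 400, but it does not say how many will carry over an unresolved AE or withdraw for one.
- That the rule targets a known high-risk group, because the Summary (Section 1, Amendment 6) admits "Subjects who discontinued from SP847 due to a dose reduction or status epilepticus, but for whom it is determined medically appropriate". The text shown does not say that those dose reductions were for AEs that persisted into SP848. SP847 also treated only 47 subjects in all.
- That a comparison between rollover and directly enrolled subjects is spoiled. The study is open-label and non-randomized, and the text shown plans no such comparison.

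**Conclusion.** The point holds in a limited form. For rollover subjects, withdrawal from SP848 due to a non-serious AE that began on LCM in the primary study and did not worsen after the first SP848 dose falls outside the primary withdrawal variable. This follows from the current definitions and needs no assumption about event rates. The direction is fixed, since any such case lowers the reported rate. The number of cases cannot be estimated from the protocol and may be small. The underlying data remain available. Separately, Sections 4.2.1.1 and 12.1.2.1 disagree on whether withdrawal is a primary variable, so this text needs an edit in any case.

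**What to change.** In Section 4.2.1.1, define the third primary safety variable as withdrawal from SP848 due to any AE. Report it on two rows: withdrawals due to TEAEs, and withdrawals due to AEs ongoing from the primary study that did not worsen in SP848. Name the same variable in Section 12.1.2.1. Leave the TEAE definition as it is for incidence.

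The cost is one line in each section and one extra table row. Carried-over AEs are already followed and the reason for withdrawal is already recorded, so no new data are needed. The reported withdrawal rate may come out slightly higher, and the TEAE-only count stays visible on its own row.
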